9.1.2.14. Laboratory Tests Used for Efficacy Measures and Disease Diagnosis

9.1.2.14.1. High Sensitivity C-Reactive Protein

High sensitivity C-reactive protein will be the measure of acute phase reactant. It will be measured with a high sensitivity assay at the central laboratory to help assess the effect of ixekizumab on disease activity.

9.1.2.15. Health Outcomes Measures

9.1.2.15.1. Healthcare Resource Utilization

Healthcare resource utilization data regarding the number of visits to medical care providers (such as general practitioners, specialists, physical, or occupational therapists, and other nonphysical care providers for services outside of the clinical trial), emergency room admissions, hospital admissions, and concomitant medications will be recorded by the investigator or designee in the study's CRF. These data will be collected to support economic evaluations of treatment.

9.1.2.15.2. Fatigue Severity Numeric Rating Scale

The fatigue severity NRS is a patient-reported single-item 11-point horizontal scale anchored at 0 and 10, with 0 representing “no fatigue” and 10 representing “as bad as you can imagine” (Naegeli et al. 2013). Patients rate their fatigue (**feeling tired or worn out**) by circling the 1 number that describes their worst level of fatigue during the previous 24 hours.

9.1.2.15.3. Medical Outcomes Study 36-Item Short-Form Health Survey

The Short Form 36 (SF-36) is a 36-item patient-reported measure designed to be a short, multipurpose assessment of health in the areas of physical functioning, role – physical, role - emotional, bodily pain, vitality, social functioning, mental health, and general health. The 2 overarching domains of mental well-being and physical well-being are captured by the Mental Component Summary and Physical Component Summary scores. The summary scores range from 0 to 100; higher scores indicate better levels of function and/or better health. Items are answered on Likert scales of varying lengths. The SF-36 version 2 (acute version) will be used, which utilizes a 1-week recall period (Ware 2000).

9.1.2.15.4. Assessment of Spondyloarthritis International Society Health Index

The ASAS–Health Index (ASAS-HI) is a disease specific health-index instrument designed to assess the impact of interventions for SpA, including axSpA. This broader concept of health is included in the International Classification of Functioning Disability and Health (ICFD) which has been published by World Health Organization (WHO). The ASAS has applied the ICFD as a basis to define a core set of items relevant for patients with axSpA. The 17-item instrument has scores ranging from 0 (good health) to 17 (poor health) (Kiltz et al. 2015). Each item consists of 1 question that the patient needs to respond to with either “I agree” (score 1) or “I do

not agree (score 0).” A score of “1” is given where the item is affirmed, indicating adverse health. All item scores are summed to give a total score or index.

9.1.2.15.5. European Quality of Life-5 Dimensions 5-Level

The European Quality of Life-5 Dimensions 5-Level (EQ-5D-5L) is a standardized measure of health status used to provide a simple, generic measure of health for clinical and economic appraisal. The EQ-5D-5L consists of 2 components: a descriptive system of the respondent’s health and a rating of his/her current health state using a 0- to 100-mm visual analog scale (VAS). The descriptive system comprises the following 5 dimensions: mobility, self-care, usual activities, pain/discomfort, and anxiety/depression. Each dimension has 5 levels: no problems, slight problems, moderate problems, severe problems, and extreme problems. The respondent is asked to indicate his/her health state by ticking (or placing a cross) in the box associated with the most appropriate statement in each of the 5 dimensions. It should be noted that the numerals 1 to 5 have no arithmetic properties and are not to be used as a cardinal score. The VAS records the respondent’s self-rated health on a vertical VAS in which the endpoints are labeled “best imaginable health state” and “worst imaginable health state.” This information can be used as a quantitative measure of health outcome. The EQ-5D-5L health states, defined by the EQ-5D-5L descriptive system, may be converted into a single summary index by applying a formula that essentially attaches values (also called weights) to each of the levels in each dimension (The EuroQol Group 2011).

9.1.2.15.6. Work Productivity and Activity Impairment Questionnaire—Spondyloarthritis

The Work Productivity Activity Impairment Questionnaire-Spondyloarthritis (WPAI-SpA) consists of 6 questions to determine employment status, hours missed from work because of spondyloarthritis, hours missed from work for other reasons, hours actually worked, the degree to which spondyloarthritis affected work productivity while at work, and the degree to which spondyloarthritis affected activities outside of work. The WPAI-SpA has been validated in the rad-axSpA patient population (Reilly et al. 2010). Four scores are derived: percentage of absenteeism, percentage of presenteeism (reduced productivity while at work), an overall work impairment score that combines absenteeism and presenteeism, and percentage of impairment in activities performed outside of work. Greater scores indicate greater impairment (Reilly Associates Health Outcomes Research [WWW]).

9.1.2.15.7. Jenkins Sleep Questionnaire

The Jenkins Sleep Evaluation Questionnaire (JSEQ) is a 4-item scale designed to estimate sleep problems in clinical research. The JSEQ assesses the frequency of sleep disturbance in 4 categories: 1) trouble falling asleep, 2) waking up several times during the night, 3) having trouble staying asleep (including waking up far too early), and 4) waking up after the usual amount of sleep feeling tired and worn out. Patients report the number of days they experience each of these problems in the past month on a 6-point Likert Scale ranging from 0 = “no days” to 5 = “22-30 days.” The total JSEQ score ranges from 0 to 20, with higher scores indicating greater sleep disturbance (Deodhar et al. 2010).

9.2. Adverse Events

An AE is defined as follows: any untoward medical occurrence in a patient or clinical investigation subject administered a pharmaceutical product that does not necessarily have a causal relationship with this treatment. An AE can, therefore, be any unfavorable and unintended sign (including an abnormal laboratory finding), symptom, or disease temporally associated with the use of a medicinal (investigational) product, whether or not related to the medicinal (investigational) product.

Investigators are responsible for monitoring the safety of patients who have entered this study and for alerting Lilly or its designee to any event that seems unusual, even if this event may be considered an unanticipated benefit to the patient.

The investigator is responsible for the appropriate medical care of patients during the study.

Investigators must document their review of each laboratory safety report.

The investigator remains responsible for following, through an appropriate health care option, AEs that are serious or otherwise medically important, considered related to the investigational product or the study, or that caused the patient to discontinue the investigational product before completing the study. The patient should be followed until the event resolves, stabilizes with appropriate diagnostic evaluation, or is reasonably explained. The frequency of follow-up evaluations of the AE is left to the discretion of the investigator.

Lack of drug effect is not an AE in clinical studies, because the purpose of the clinical study is to establish treatment effect.

After the informed consent form (ICF) is signed, study site personnel will record via case report form (CRF) the occurrence and nature of each patient's preexisting conditions, including clinically significant signs and symptoms of the disease under treatment in the study. In addition, site personnel will record any change in the condition(s) and any new conditions as AEs. Investigators should record their assessment of the potential relatedness of each AE to protocol procedure, investigational product, via CRF.

The investigator will interpret and document whether or not an AE has a reasonable possibility of being related to study treatment, study device, or a study procedure, taking into account the disease, concomitant treatment or pathologies. To assess the relationship of the AEs, the following is defined:

Reasonably Possibly Related: Reasonable possibility that there is a cause and effect relationship between the study product and/or study procedure and the AE.

The investigator answers yes/no when making this assessment.

Planned surgeries and nonsurgical interventions should not be reported as AEs unless the underlying medical condition has worsened during the course of the study.

If a patient's investigational product is discontinued as a result of an AE, study site personnel must report this to Lilly or its designee via electronic data entry, clarifying if possible, the circumstances leading to any dosage modifications, or discontinuations of treatment.

Accurate start and stop dates (and times, where required) are to be reported via electronic data entry for all AEs. Only AEs that are ongoing at the last study visit and/or communication are to be documented as "ongoing."

9.2.1. Serious Adverse Events

An SAE is any AE from this study that results in one of the following outcomes:

- death
- initial or prolonged inpatient hospitalization
- a life-threatening experience (i.e., immediate risk of dying)
- persistent or significant disability/incapacity
- congenital anomaly/birth defect
- considered significant by the investigator for any other reason: important medical events that may not result in death, be life-threatening, or require hospitalization may be considered serious, based upon appropriate medical judgment.

Although all AEs occurring after signing the ICF are recorded in the CRF, SAE reporting begins after the patient has signed the ICF and has received investigational product. However, if an SAE occurs after signing the ICF, but prior to receiving investigational product, it needs to be reported ONLY if it is considered reasonably possibly related to study procedure.

Study site personnel must alert Lilly or its designee of any SAE within 24 hours of investigator awareness of the event via a sponsor-approved method. If alerts are issued via telephone, they are to be immediately followed with official notification on study-specific SAE forms. This 24-hour notification requirement refers to the initial SAE information and all follow-up SAE information.

Pregnancy (during maternal or paternal exposure to investigational product) does not meet the definition of an AE. However, to fulfill regulatory requirements any pregnancy should be reported following the SAE process to collect data on the outcome for both mother and fetus.

Investigators are not obligated to actively seek AEs or SAEs in patients once they have discontinued and/or completed the study (the patient summary CRF has been completed). However, if the investigator learns of any SAE, including a death, at any time after a patient has been discharged from the study, and he/she considers the event reasonably possibly related to the study treatment or study participation, the investigator must promptly notify Lilly.

9.2.1.1. Suspected Unexpected Serious Adverse Reactions

Lilly has procedures that will be followed for the recording and expedited reporting of suspected unexpected serious adverse reactions (SUSARs) that are consistent with global regulations and the associated detailed guidances.

9.2.2. Adverse Events of Special Interest

The following adverse events of special interest (AESIs) will be used to determine the safety and tolerability of ixekizumab over the range of doses selected for this clinical study.

Adverse events of special interest for ixekizumab are as follows:

- cytopenias (leukopenia, neutropenia, and thrombocytopenia)
- clinically significant hepatic events and/or significant elevations in liver function test changes/enzyme elevations (ALT, AST, bilirubin, and alkaline phosphatase)
- infections
- injection-site reactions
- allergic reactions/hypersensitivities
- cerebrocardiovascular events
- malignancies
- inflammatory bowel disease
- depression

Sites will provide details on some of these AEs as instructed on the CRF. Investigators will also educate patients and/or caregivers about the symptoms of allergic/hypersensitivity reactions and will provide instructions on dealing with these reactions (see also Section 7.1.2). A blood sample will be collected as soon as possible for any patient who experiences an AE of a potential systemic allergic/hypersensitivity reaction during the study as judged by the investigator.

Data on preferred terms associated with cerebrocardiovascular events (defined as death, cardiac ischemic events including MI and hospitalization for unstable angina, hospitalization for heart failure, serious arrhythmia, resuscitated sudden death, cardiogenic shock, coronary revascularization procedure, stroke/transient ischemic attack, peripheral revascularization procedure, peripheral arterial event, and hospitalization for hypertension) will be collected, and these events and any deaths will be adjudicated by an external clinical events committee (CEC) made up of a chairman, 2 cardiologists, and a neurologist. The role of the CEC will be to adjudicate these defined clinical events in a blinded, consistent, and unbiased manner throughout the course of a study and ensure that all events that have been reported are evaluated uniformly by a single group (the CEC).

Data on suspected IBD, as identified by events possibly indicative of ulcerative colitis and Crohn's disease, will be collected and the events will be adjudicated by an external CEC with expertise in IBD. The role of the CEC will be to adjudicate defined clinical events, in a blinded, consistent, and unbiased manner throughout the course of a study and ensure that all events that have been reported are evaluated uniformly by a single group.

9.2.3. Complaint Handling

Lilly collects product complaints on investigational products and drug delivery systems used in clinical studies in order to ensure the safety of study participants, monitor quality, and to facilitate process and product improvements.

Patients will be instructed to contact the investigator as soon as possible if he or she has a complaint or problem with the investigational product so that the situation can be assessed.

9.3. Treatment of Overdose

Refer to the IB and/or the product label where applicable.

9.4. Safety

9.4.1. *Electrocardiograms*

For each patient, electrocardiograms (ECGs) should be collected according to the Schedule of Activities (Section 2). Patients are to be resting for 5 minutes prior to the ECG. It is recommended that patients be in a supine position.

Any clinically significant findings from ECGs that result in a diagnosis and that occur after the patient receives the first dose of the investigational treatment should be reported to Lilly or its designee as an AE via CRF.

9.4.2. *Vital Signs*

For each patient, vital signs measurements (sitting) should be conducted according to the Schedule of Activities (Section 2). Vital signs include blood pressure (BP), pulse, and temperature. Patients are to be resting for a minimum of 5 minutes prior to vital sign collection.

Any clinically significant findings from vital signs measurement that result in a diagnosis and that occur after the patient receives the first dose of study treatment should be reported to Lilly or its designee as an AE via CRF.

9.4.3. *Laboratory Tests*

For each patient, laboratory tests detailed in (Appendix 2) should be conducted according to the Schedule of Activities (Section 2). Please reference the central laboratory manual for specific instructions.

Urine pregnancy test will be collected and read/analyzed locally. Urine testing for pregnancy may occur at intervals more frequently than according to the Schedule of Activities during the study treatment period and/or follow up period if required per local regulation.

Any clinically significant findings from laboratory tests that result in a diagnosis and that occur after the patient receives the first dose of investigational product should be reported to Lilly or its designee as an AE via CRF.

9.4.4. *Physical Examination*

For each patient, a complete physical examination must be conducted according to the Schedule of Activities (Section 2).

Any clinically significant finding from a complete physical examination that results in a diagnosis and that occurs after the patient receives the first dose of study treatment is to be reported to Lilly or its designee as an AE via CRF.

9.4.5. Eye Symptom Assessment

At each study visit, study healthcare providers will evaluate the patient for any symptoms of anterior uveitis as specified in the Schedule of Activities (Section 2). If the patient has no prior ophthalmologist diagnosed anterior uveitis and develops eye pain or discomfort, eye redness, blurring of vision, or any other symptoms suggestive of anterior uveitis, the patient must be evaluated by an ophthalmologist. If a patient has prior history of ophthalmologist diagnosed anterior uveitis, then she/he must be evaluated by a physician for recurrence of anterior uveitis (whenever possible, diagnosis is to be confirmed by an ophthalmologist).

9.4.6. Tuberculosis Testing

Tuberculosis testing will be conducted based on clinical assessment of TB risk (symptoms/signs/known or suspected TB exposure), and as required by local regulations and/or local standard of care.

Patients with a positive TB test and/or other evidence of active TB should be discontinued (Section 8.1.1).

In patients with a positive TB test indicating TB test conversion since prior testing (based on patient medical history), but no other evidence of active TB, study treatment should be withheld. These patients may continue in Study RHBY and resume study treatment without repeating TB testing if all of the following conditions are met:

- a specialist in the care of patients with TB (e.g., infectious disease or pulmonary medicine subspecialists) is consulted and does not identify evidence of active TB, and the patient is assessed as having latent TB infection
- a posterior-anterior view chest x-ray or results from a chest x-ray obtained within 30 days prior to the positive TB test does not indicate active TB infection
- after receiving at least the initial 4 weeks of appropriate latent TB infection (LTBI) therapy with no evidence of hepatotoxicity (ALT/AST must remain $\leq 2 \times \text{ULN}$) upon retesting of serum ALT/AST
- meet all other inclusion/exclusion criteria for participation

Such patients must complete appropriate LTBI therapy in order to remain in compliance and continue to participate in the study.

If a positive TB test result is believed to represent a false-positive result based on thorough medical assessment of the patient, the investigator should discuss further testing and management with Lilly medical.

Any findings of a positive TB test that occurs after the patient receives the first dose of study treatment are to be reported to Lilly or its designee as an AE via CRF.

9.4.7. *Quick Inventory of Depressive Symptomatology—Self-Report (16 Items)*

For each patient, a QIDS-SR16 assessment will be collected according to the Schedule of Activities (Section 2).

Any clinically significant findings from the QIDS-SR16 assessment that result in a diagnosis and that occur after the patient receives the first dose of study treatment are to be reported to Lilly or its designee as an AE via CRF.

The QIDS-SR16 is a self-administered 16-item instrument intended to assess the existence and severity of symptoms of depression as listed in the American Psychiatric Association's Diagnostic and Statistical Manual of Mental Disorders, 4th Edition (APA 1994). A patient is asked to consider each statement as it relates to the way they have felt for the past 7 days. There is a 4-point scale for each item ranging from 0 to 3. The 16 items corresponding to 9 depression domains are summed to give a single score ranging from 0 to 27, with higher scores denoting greater symptom severity. The domains assessed by the instrument are (1) sad mood, (2) concentration, (3) self-criticism, (4) suicidal ideation, (5) interest, (6) energy/fatigue, (7) sleep disturbance (initial, middle, and late insomnia or hypersomnia), (8) decrease/increase in appetite/weight, and (9) psychomotor agitation/retardation. Additional information and the QIDS-SR16 questions may be found at the University of Pittsburgh IDS/QIDS internet page (IDS/QIDS home page [WWW]).

9.4.8. *Columbia Suicide Severity Rating Scale*

The C-SSRS (Posner et al. 2007; C-SSRS web site [WWW]) is a scale that captures the occurrence, severity, and frequency of suicide-related ideations and behaviors during the assessment period. The C-SSRS must be administered by appropriately trained site personnel. The tool was developed by the National Institute of Mental Health Treatment of Adolescent Suicide Attempters trial group for the purpose of being a counterpart to the Columbia Classification Algorithm of Suicide Assessment categorization of suicidal events. Patients will be assessed according to the Schedule of Activities (Section 2).

The Self-Harm Supplement Form is a one-question form that is completed at any visit, including baseline visits, asking for the number of suicidal or nonsuicidal self-injurious behaviors the patient experienced since last assessment. For each unique event identified, a questionnaire (Self-Harm Follow-Up Form) which collects supplemental information on the self-injurious behavior must be completed. This information is then documented in the eCRF.

9.4.9. *Immunogenicity*

For each patient, an immunogenicity sample will be collected according to the Schedule of Activities (Section 2). If necessary, samples may also be tested for ixekizumab drug concentrations to facilitate the interpretation of the immunogenicity data.

Additionally, a blood sample will be collected, as soon as possible, for any patient who experiences a potential systemic allergic/hypersensitivity reaction during the study as judged by the investigator. These samples will be tested for immunogenicity and PK, while other

laboratory tests may be performed as needed to elucidate the cause of the allergic/hypersensitivity reaction.

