- [3] The patient experiences a severe AE, an SAE, or a clinically significant change in a laboratory value that, in the opinion of the investigator, merits the discontinuation of the investigational product and appropriate measures being taken. In this case, Lilly or its designee is to be notified immediately. Refer to AEs, Section 9.2.
- [4] Any positive TB test that indicates TB test conversion since prior testing (based on patient medical history), AND the patient does not receive appropriate treatment for latent TB; or there is evidence of active TB infection at any time.
- [5] Clinically significant systemic hypersensitivity reaction following SC administration of investigational product that does not respond to symptomatic medication or results in clinical sequelae.
- [6] The patient becomes pregnant.
- [7] The patient develops a malignancy.

Note: Patients may be allowed to continue if they develop no more than 2 nonmelanoma skin cancers during the study.

- [8] Enrollment in any other clinical trial involving an investigational product or enrollment in any other type of medical research judged not to be scientifically or medically compatible with this study.

[9] It is recommended that the patient is assessed by a psychiatrist or appropriately trained professional to assist in deciding whether the patient is to be discontinued from the study in the following circumstances:

The patient, at any time during the study, scores a 3 for Item 12 (Thoughts of Death or Suicide) on the Quick Inventory of Depressive Symptomatology-self report (16 items) (QIDS-SR16);

OR

develops active suicidal ideation with some intent to act with or without a specific plan (yes to question 4 or 5 on the “Suicidal Ideation” portion of the Columbia-Suicide Severity Rating Scale [C-SSRS]);

OR

develops suicidal behaviors as recorded on the C-SSRS.

[10] The investigator or attending physician decides that the patient is to be withdrawn from study treatment.

[11] The patient requests to be withdrawn from study treatment.

[12] Lilly or its designee stops the patient’s participation in the study or Lilly stops the study for medical, safety, regulatory, or other reasons consistent with applicable laws, regulations, and good clinical practice (GCP).

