[D3] In the opinion of investigator, if a patient experiences a severe AE, an SAE, or a clinically significant change in a laboratory value that merits the discontinuation of the investigational product and appropriate measures being taken.	Monitor	From monitor's list
[D4] Any positive TB test and the patient does not receive appropriate treatment for latent TB; or there is evidence of active TB infection at any time	Monitor	From monitor's list.
[D5] Clinically significant systemic hypersensitivity reaction that does not respond to treatment	Monitor	From monitor's list
[D6] Patient became pregnant	Monitor	From monitor's list
[D7] Patient developed a malignancy (Patients may be allowed to continue if they develop no more than 2 nonmelanoma skin cancers during the study)	Monitor	From monitor's list

Important Protocol Deviation Category/Subcategory/Study Specific	Source to Identify Protocol Deviationa	Statistical Programming Guidance for Clinical Study Report
[D8] Enrolled in prohibited medical research	Monitor	From monitor's list
[D12] Lilly stopped the patient participation	Monitor	From monitor's list
[D13] Patient became HBV DNA positive	Monitor/stats	From monitor's list, or stats program based on HBV DNA records.
[D14] Patient has a confirmed diagnosis of PCP during the study for patients from Japan sites	Monitor	From monitor's list
Category: Study Procedures		
Subcategory: Excluded Con-meds	Monitor	Either from monitor's list .
Subcategory: Lab/Imaging Criteria		
Missing lab chemistry and hematology: missing at Week 0, or not having at least 1 visit after Week 0.	Stats	If missing at Week 0 from RHBY, or not having at least 1 visit after Week 0 from RHBY.
Subcategory: Other		
Missing QIDS total score: missing at Week 0 or not having at least one scheduled visit in each period.	Stats	If missing QIDS total score at Week 0 or not having at least one scheduled visit in each period
Missing Columbia scale score at any visit	Monitor and Stats	From monitor's list; if missing Columbia scale at any visit
Incorrect IWRS entries of partial ASDAS scores or CRP resulting in errors to define sustained remission status during Period 1 or the 1st flare at the post-randomization visits during Period 2 and Periods 2 and 3 combined	Monitor	From monitor's list, Stats will use program to support for data checking
Had unqualified site personnel perform clinical safety and/or efficacy assessments	Monitor	From monitor's list

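### Protocol 9.4.6 discontinues on any positive TB test, which is broader than the stopping criterion it cites (8.1.1 [4]) and at odds with its own withhold-and-resume paragraph

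*Protocol*

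**What the plan says.** Protocol 9.4.6 (Tuberculosis Testing) makes testing depend on clinical risk, local regulations and standard of care. It then gives three instructions about a positive result.

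- A general sentence, with a reference to Section 8.1.1: "Patients with a positive TB test and/or other evidence of active TB should be discontinued".
- A paragraph that begins "In patients with a positive TB test indicating TB test conversion since prior testing" and is limited to patients without other evidence of active TB. Treatment is withheld, and then: "These patients may continue in Study RHBY and resume study treatment without repeating TB testing if all of the following conditions are met". The conditions are specialist review, chest x-ray, at least 4 weeks of latent TB therapy with ALT/AST within a limit, and the remaining eligibility criteria.
- A later paragraph that begins "If a positive TB test result is believed to represent a false-positive result based on thorough medical assessment of the patient" and sends the investigator to the sponsor's medical staff.

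Protocol 8.1.1 criterion [4] lists permanent discontinuation for a positive test showing conversion, "AND the patient does not receive appropriate treatment for latent TB; or there is evidence of active TB infection at any time".

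Protocol 8.1.2 (temporary discontinuation) and 7.4 (dosage modification) refer only to 9.4.10.1, the neutropenia section, for withholding drug. Section 7.4 adds that, apart from the exceptions it names, dose modification is not allowed.

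SAP 6.15, Table RHBY.6.11, row [D4], under violation of discontinuation criteria, reads "Any positive TB test and the patient does not receive appropriate treatment for latent TB", or evidence of active TB. Its source is the monitor's list.

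**The concern.** The general sentence in 9.4.6 uses and/or, so on its face a positive test is enough to discontinue. The section it cites does not say that, and the next paragraph of 9.4.6 describes patients with a positive test who stay in the study and restart treatment. Nothing such as except or unless links the two. A site that follows the general sentence and a site that follows criterion [4] could therefore treat the same patient differently in a safety matter.

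There are two smaller consequences. A site that looks up temporary discontinuation in 8.1.2 or 7.4 will not find the TB withholding. And [D4] describes a wider trigger than criterion [4], so the important-deviation summary could include patients who broke no stopping criterion.

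The statistical link is indirect. Under nonresponder imputation (Protocol 10.3.1.5.1, SAP 6.3.1), a Group B patient who discontinues study treatment in Period 2 for any reason is counted as a flare. A patient whose treatment is withheld and later resumed is not counted that way automatically.

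**Working it through.** No figure is at issue, so the check is to apply each rule to the same patient types.

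| Patient | 9.4.6 general sentence | Other paragraphs of 9.4.6 | 8.1.1 [4] | SAP [D4] trigger |
|---|---|---|---|---|
| (a) Converted, no active TB, latent TB treated | Discontinue | Withhold; may resume if all conditions are met | Not met | Not met |
| (b) Positive but not a conversion, no active TB, no latent TB treatment | Discontinue | Not covered | Not met | Met |
| (c) Suspected false positive, no latent TB treatment | Discontinue | Discuss with sponsor | Met only if the result counts as a conversion | Met |
| (d) Converted, no active TB, latent TB not treated | Discontinue | Withhold; resume conditions not met | Met | Met |
| (e) Active TB | Discontinue | Resume route does not apply | Met | Met |

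1. In (d) and (e) the general sentence, criterion [4] and [D4] agree, and the resume route is closed.
2. In (a) the general sentence stands alone. Criterion [4], the resume paragraph and [D4] are all compatible with the patient continuing.
3. In (c) the general sentence conflicts with the false-positive paragraph.
4. In (b) the general sentence and criterion [4] give opposite answers, and no other protocol paragraph settles the matter. This is also where [D4] departs from criterion [4]: a patient who is kept on treatment consistently with [4] fits the description of a deviation.

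The TB withholding in 9.4.6 appears in neither 8.1.2 nor 7.4, because both refer to 9.4.10.1 alone.

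On size, the documents give no rate of positive tests, and testing is not routine. The number of affected patients therefore cannot be computed.

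**The case against.** The strongest reply is that 9.4.6 states a general rule and then its special cases. The general sentence points to 8.1.1, the conversion paragraph repeats the phrase about other evidence of active TB and so marks out a subset, and false positives have their own paragraph. Read this way, (a) and (c) are settled. That much stands. It does not settle (b), and it leaves the general sentence wider than the criterion it cites.

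A reader might infer that the documents hold four rival rules. They do not: criterion [4] and the resume paragraph broadly agree, and the outlier is the general sentence.

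A reader might also infer that the SAP gives sites a further instruction. It does not. Table RHBY.6.11 classifies deviations, [D4] is taken from the monitor's list, and other rows are shortened too ([D5] leaves out the clinical-sequelae part of criterion [5]). The mismatch concerns reporting only.

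On safety, dosing stops for a converted patient under either 9.4.6 instruction, and resumption is guarded by several conditions. The conflict there is between permanent discontinuation and a withholding that may end. It is not a case of one instruction letting dosing go on unchecked.

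**Conclusion.** The point holds as a wording inconsistency in a safety section. The general sentence of 9.4.6 is broader than 8.1.1 [4], conflicts on its face with the paragraphs after it, and leaves a positive test that is not a conversion under opposite instructions. The omissions in 8.1.2 and 7.4 are part of the same problem. The [D4] wording is a secondary reporting point.

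Its statistical weight is small. It is tempting to say that each affected Group B patient becomes either a completer or an imputed flare, so that the primary endpoint is at risk. The documents do not support that. A patient whose treatment is withheld may still flare, may fail the resume conditions or may stop for another reason. Period 2 treatment is randomized and blinded in Group B, and nothing in the plan suggests that the ambiguity would act differently between arms. The view that few patients are affected is a judgement from risk-based testing, not a figure in the documents.

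No position is taken on which clinical rule is right.

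**What to change.** Reconcile the general sentence of 9.4.6 with its following paragraphs and with 8.1.1 [4], so that one rule is stated throughout. Say explicitly how the general sentence relates to the converted-test and false-positive paragraphs, and which instruction applies to a positive test that is not a conversion. Add a reference to the TB withholding in 8.1.2 and 7.4, if withholding remains part of the rule. Then word SAP [D4] to match criterion [4] as finally agreed. The sponsor's medical team should decide the clinical content.

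The cost is wording in four protocol sections and one SAP table row. Sample size, data collection and analysis methods do not change.
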